#### ***Adverse Events and Serious Adverse Events***

An adverse event is the appearance or worsening of any undesirable sign, symptom, or medical condition occurring after starting the investigational component even if the event is not considered to be related to study component. Medical conditions/diseases present before starting study component are only considered adverse events if they worsen after starting study drug. Abnormal laboratory values or test results constitute adverse events only if they induce clinical signs or symptoms, are considered clinically significant, or require therapy.

The investigator (or physician designee) is responsible for verifying and providing source documentation for all adverse events and assigning the attribution for all adverse events for subjects enrolled. The physician may delegate to other members of the medical team the task of a preliminary review of the adverse event, attribution, and recommended action plan. The physician will then complete the final review of the adverse event, confirm attribution and sign off on the adverse events. Since this is an ITP study, safety will be monitored by the MD Anderson IND Office. Adverse event terminology and grades will be determined using the Common Terminology Criteria for Adverse Events (CTCAE), version 5.0, published by the U.S. Department of Health and Human Services. Adverse events will be reviewed by our medical personnel and the PI. Adverse event monitoring will continue up to 30 days after medication is completed. If an AE is spontaneously reported after the AE reporting period is over, the AE will be recorded in the patient's progress notes. Those AEs that are probably, possibly or definitely related to treatment will be followed until resolution or end of study, whichever comes first. In the case of reports of suicidal ideation, depression or anxiety which we believe may be related to treatment, if possible, we will engage in our normal psychological assessments. The Addiction Psychiatrist will determine the course of clinical management according to methods of good clinical practice. The PI or physician is responsible for determining the final attribution of adverse events to study medication.

Based on the new safety information related to vaping and e-cigarette use, this protocol will be reviewed every 6 months for safety monitoring by IRB Continuing Review and MD Anderson's Data Safety Monitoring Board (DSMB).

**Adverse experiences associated with specimen collection.** The collection of urine by the participants using specimen cups are not expected to result in adverse events.

**Adverse experiences associated with electronic cigarettes.** Use of ECs has been found to increase the risk of acute upper respiratory irritation, cough, phlegm production, headache, dry mouth/throat, vertigo, and nausea . Participants using SRECs, particularly the placebo version, may experience nicotine withdrawal effects, including increased irritability, difficulty concentrating, insomnia, anxiety, dysphoria, and hunger. None of these effects should result in serious adverse health consequences. However, it is possible that e-cigarettes may cause lung injuries or other serious health problems, which study medical monitor [name] and his team will monitor, along with our collaborator from the Department of Pulmonary Medicine, [name].

In the event of a new health risk associated with the electronic cigarettes used in this protocol that is identified, we will take the following steps: (1) the newly identified risk will be discussed within 5 days by study chair [name], collaborator and Study Physician [name], pulmonology collaborator [name], and collaborator [name] to determine its relevance to the study products used in this protocol; (2) if the risk is deemed by the collaborators to be related to the study products used in this protocol, we will contact all active subjects by phone within 5 days and submit a PI memo to MD Anderson's IRB and IND offices that describes this new health risk (also within 5 days); (3) Upon determination by the IRB, the protocol and ICD will be revised to incorporate information about the newly identified risk, the DSMB will be informed at the next semi-annual review of this protocol, and active participants will be reconsented with the details of these new risks. We will keep a log of any new risks communicated by the CDC and/or the Texas HHS that are deemed relevant to the study products used in this protocol, including participants who are contacted and/or reconsented and the date of this contact.

**Adverse experiences associated with questionnaires.** It is unlikely that completing questionnaires would lead to any potential risks for participants, although some participants may

be uncomfortable answering certain questions and may refuse to do so. To the extent that answers to these questions are required for study participation (e.g., psychiatric and medical history), participants who do not wish to answer will not be eligible for participation. It is highly unlikely that any legal, social, or psychological problems will result from this research.

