**Phases 2 & 3: SREC-NIC and SREC-PLA use (weeks 3-4, 5-6).** During Phases 2 & 3, participants will be provided with SREC-NIC or SREC-PLA, in a counter-balanced fashion (i.e., half will receive SREC-NIC during phase 2 and SREC-PLA during phase 3). The subjects will be randomized on a 1:1 ratio and will be assigned to their randomization group through the protocol specific TRTP database. 50% (70 subjects) will receive the Active study product first and the placebo second and 50% will receive the Placebo study product first and the active study product second. During the randomization process, participants will be stratified by gender for order of exposure to SREC-PLA and SREC-NIC. At the beginning of each phase, each participant will receive 2 SREC devices with non-removable rechargeable batteries (3.3 v, 1000 mAh battery), 1 USB recharger, a 2-week supply of sealed SREC tanks (14 pods; containing either nicotine or placebo e-liquid), a user manual, and a carrying pouch. The SRECS are produced by NJOY LLC (Glenns Ferry, ID) under NIDA contract, and are available in two nicotine doses, 5% (~59 mg/ml nicotine) and 0% (0 mg/mL nicotine; placebo), a single flavor (nicotine), and in sealed disposable pods that deliver <350 puffs/pod . Participants will be instructed to use the SREC during Phases 2 and 3 whenever they get the urge to smoke, but will not be penalized for using their UB CCs or other nicotine products (including other ECs), as product use is a dependent measure in this study. The use of UB CCs and the study products will be documented daily by the participant in Qualtrics as part of the EMA.

At the beginning Phase 2, participants will receive training in how to use the SREC product. They may be shown a brief video demonstrating its use followed by a hands-on training which will include assembly (battery and tank), turning the SREC on and off, puffing, and recharging the battery. The training session will last 30 minutes and will include a minimum of three bouts of 10 puffs each in which the user will be encouraged to vary puff topography to maximize desired sensory qualities of product use. This procedure is currently being used by us in our active EC grant (R01DA042526), and has been found to result in users achieving

**Figure 1.** Timeline of study procedures.

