condition. The Program Director, who will not have participant contact, will manage the inventory and labeling of blinded products. Blinded study staff will distribute the product to patients at each visit. The study medical monitor ([name]) and collaborator on respiratory symptom assessment ([name]) will be provided unblinded information on SREC condition by the Program Director, per their request. In the case an unblinding needs to occur, the study team will notify the IND sponsor Clinical Trials Safety Team, the DSMB, and the IRB. The SRECs will be obtained through NIDA's procurement process.

Measures specific to these phases will be captured at in-person or virtual visits at the end of each phase (weeks 4 & 6). Daily smartphone EMA assessments will occur throughout all phases.

**COVID-19 adaptation:** Participants will be mailed their 2-week allotment of study ECIGs prior to the start of phases 2 and 3 by a study staff member blinded to the nicotine dose. Additionally, participants will be asked to provide the urine samples during each phase and mail those back to the primary MD Anderson site. All supplies to collect the samples, as well as shipping materials and postage will be provided. Visit payment will be issued once MD Anderson staff are able to track movement on the return package. Alternatively, participants may be asked to collect the study ECIGs and/or provide their urine samples in-person from an approved site. Approved sites may include University of Texas MD Anderson, University of Texas sister institutions including the Center for Neurobehavioral Research on Addiction (CNRA) at University of Texas Medical School, other universities or hospitals located in Texas, and/or contracted commercial vendors.

**Study Supply Kit: Treatment visits.** The following items are included in each treatment visit study kit.

- Urine collection kit
- Return address label, postage-paid, and box for shipment
- Biospecimen bag, absorbant test tube sleeves
- e-cigarette kit
- Written instructions

Treatment study kits will be mailed approximately 5-7 days prior to each treatment visit. Mailing time may be adjusted due to carrier delays, holidays, or any other factor impacting delivery time. Participants will be instructed to complete the required visit samples and place in the mail to be returned to MD Anderson.

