**Consideration of Relevant Biological Variables.** We will recruit an equal number of male and female adult daily smokers for this study because gender differences form the main focus of this proposal. While biological sex is the primary independent variable, we will also account for other relevant biological variables, such as age, by including them as covariates of interest in our statistical models. We are using multilevel models to partially pool the estimate from each covariate toward the overall mean of all estimates. This is a natural away to account for multiple comparisons without sacrificing power (which we do in the case of Bonferroni correction). Each effect is shrunk toward the overall estimate. The higher the uncertainty of a specific effect the more it shrinks toward the overall estimate.

**Timetable.** After a 3-month study setup, we expect to enroll between months 6 and 20, at a rate of 10 subjects per month (see **Table 3**). The final participant session will be during month 22, and data analysis and initial manuscript drafting will occur by month 24.

**Future directions.** At the project's conclusion, we will be able to provide scientific information on gender differences in terms of the extent to which the NIDA SREC is used and accepted by adult CC smokers, which would indicate whether it could serve as a good model of future EC research. We will also identify factors that moderate or mediate the effects of switching to nicotine and placebo SRECs from CCs. Our next steps will be to submit proposals

hormonal contraception. However, we will capture self-report of both factors and use them as moderators (hormonal contraceptive use) and mediators (menstrual phase) as part of the exploratory aim.

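### When a new risk is judged related to the study e-cigarettes, the IRB and IND offices are told within days but the DSMB only at its next six-monthly review

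*Combined protocol and SAP*

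**What the plan says.** All references are to the combined protocol and SAP. The section Adverse Events and Serious Adverse Events, in its paragraphs on electronic cigarettes, sets out three steps for a new health risk.

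- Step 1: "the newly identified risk will be discussed within 5 days by study chair" and named collaborators, who decide whether it bears on the study products.
- Step 2, if it does: "we will contact all active subjects by phone within 5 days and submit a PI memo to MD Anderson's IRB and IND offices". The memo carries the same 5-day limit as the calls.
- Step 3, once the IRB has made its determination: the protocol and consent document are revised, and those still in the trial consent again ("active participants will be reconsented with the details of these new risks"). On the monitoring board, this step says only that "the DSMB will be informed at the next semi-annual review of this protocol".

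The same section fixes the interval: "this protocol will be reviewed every 6 months for safety monitoring by IRB Continuing Review", and the sentence goes on to name the institution's DSMB alongside the IRB. It gives recent safety information on vaping as the reason for that frequency, and it names the IND Office as the body that monitors safety.

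Elsewhere, the blinding text under Procedures says that if an unblinding is needed, "the study team will notify the IND sponsor Clinical Trials Safety Team, the DSMB, and the IRB". The Timetable paragraph under Potential Problems & Alternative Strategies says "we expect to enroll between months 6 and 20, at a rate of 10 subjects per month".

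**The concern.** The rule applies only after the team has decided that the risk concerns the product participants are using. Of the oversight bodies named in the protocol's safety text, the DSMB is the one left off the 5-day memo, although the six-monthly schedule it shares with the IRB was adopted because of vaping safety news. This is a stated rule, not a missing detail.

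At stake is the board's ability to look at the trial's accumulating data for the signal, and to advise, while participants are still being exposed. The heading "SREC-NIC and SREC-PLA use (weeks 3-4, 5-6" puts SREC use at four weeks per participant, after a two-week baseline. Several successive groups of participants could therefore start and finish product use within one interval between board reviews.

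The calls and the reconsent cover active subjects only. This is a separate and smaller matter. Someone who used the product and has finished is given no prompt to watch for, or report, late symptoms.

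**Working it through.** **Inputs**
- Board interval: 6 months (Adverse Events and Serious Adverse Events).
- Time to the IRB and IND offices: 5 days to discuss plus 5 days to notify, so at most 10 days from identification (same section).
- Enrolment: 10 per month over months 6 to 20, that is 14 months (Timetable).
- Number randomised: 164, for 140 after 15% dropout (Power and Sample Size). Recruitment ceiling: 196 (Participants).
- SREC use: weeks 3 to 6, 28 days (Procedures).
- One month is taken as 365.25/12 = 30.44 days. Enrolment is assumed steady and is not paused. Dropout is ignored in the counts.

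**1. The plan's own figure.** 140 / (1 − 0.15) = 164.7, against 164 stated. This reproduces to rounding and serves here only as a denominator.

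**2. Enrolment during the wait for the DSMB, at the stated rate.**
- Longest wait: 10 × 6 = 60; 60/164 = 36.6%.
- Average wait, if the risk arises at a random point between reviews (an assumption): 10 × 3 = 30; 30/164 = 18.3%.

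**3. Sensitivity to the rate.** The timetable does not reach the stated sample: 10 × 14 = 140, not 164 or 196. For that reason 60 is 37% of 164 but 43% of the 140 that the timetable yields (6/14 = 42.9%).

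| Enrolment rate | Maximum in 6 months | Mean (3 months) |
|---|---|---|
| 10 per month (stated) | 60 | 30 |
| 164/14 = 11.7 per month | 70 | 35 |
| 196/14 = 14 per month | 84 | 42 |

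**4. Enrolled versus exposed.** Product use begins two weeks after enrolment, so at 10 per month about 10 × 14/30.44 = 4.6 of the 60 would still be in baseline when the board meets. A similar number, already in baseline when the risk was judged, would start product meanwhile. New starters over six months are therefore also about 60 under steady enrolment. About 10 × 28/30.44 = 9.2 more are on product at any time; these are active subjects and would be phoned.

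**5. If the DSMB shared the IRB and IND clock.** Over at most 10 days, 10 × 10/30.44 = 3.3 participants would start product before the board knew (3.8 at 11.7 per month, 4.6 at 14 per month), against the present maxima of 60, 70 and 84.

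**6. Finished participants.** Seven months into enrolment, 70 have enrolled. Those past day 42 have finished SREC use: 10 × (7 − 42/30.44) = 56. Those past day 72 are also beyond the 30-day safety call: 10 × (7 − 72/30.44) = 46. How many of these 46 to 56 would be contacted depends on what *active* means.

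**7. Other routes to the DSMB.** The serious adverse event sections send reports to the IND Office (within 24 hours), the IRB, FDA and NIDA; they do not name the DSMB. Protection against Risks refers to a Data and Safety Monitoring Plan section that is in neither the contents list nor the text available. A faster route there cannot be ruled out, but it would then conflict with step 3.

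**The case against.** The strongest reply is that oversight does not wait for the DSMB. Collaborators, including pulmonology, meet within 5 days. The IRB, the IND Office and every active subject hear within 5 days after that, and reconsent follows the IRB's determination. The medical monitor oversees adverse event review and, with the respiratory collaborator, can obtain unblinded condition on request. All of this stands. A reader might infer from the 60 that participants would be exposed with nobody watching; the documents do not support that.

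Three other inferences go too far.

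- *That the protocol gives a single unblinding faster notice than a product risk.* The unblinding text names the DSMB but sets no deadline, so it shows a different route, not a shorter clock, and the two passages do not contradict each other. Nor was the board created for vaping risk: only the review frequency is tied to it, and the IRB shares that schedule.
- *That finished participants cannot report late symptoms.* The protocol provides for recording events reported spontaneously after the reporting period, and requires related serious events after 30 days to go to the IND Office. What is missing is the prompt.
- *That limiting contact to active subjects adds to exposure before the DSMB knows.* It cannot, because those left out have already stopped using study product. The term may also cover people awaiting the 30-day call.

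None of this explains why the board should be left off a memo that is already being sent.

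**Conclusion.** The point holds as a gap in DSMB notice. The wait is 0 to 6 months, while the IRB and IND offices wait at most 10 days. Up to 60 further participants (37% of 164), and about 30 on average, could enrol in that time at the stated rate. The maximum rises to 70 or 84 if accrual is fast enough to reach 164 or 196 in 14 months.

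These figures rest on steady enrolment. The maximum also needs the risk to be judged just after a board review, with the IRB, the IND Office and the study team all leaving enrolment unchanged. The average assumes random timing between reviews. No endpoint, sample size or analysis is affected. The case for acting is that a safety board would learn of a product risk promptly at almost no cost. The contact of finished participants is a lesser clarification and should be handled on its own.

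**What to change.** 1. In step 2 of the new-risk procedure, add the DSMB as a recipient of the same memo, on the same 5-day limit as the IRB and IND offices. In step 3, delete the deferral to the semi-annual review. Any decision on continuing stays with the DSMB and IRB. If the Data and Safety Monitoring Plan exists as a separate text, bring it into line. Cost: one more recipient and a possible unscheduled DSMB look, arising only if a risk is judged related.

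2. Separately, define *active*, and extend the notice to everyone who received SREC product, with a line on how to report late symptoms. Cost: brief calls or messages to finished participants, again only if a risk is confirmed.

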### ***Specific Instructions for Adverse Events Recording***

For this project, adverse events will be recorded according to the Recommended Adverse Event Recording Guidelines for Phase III protocols (see **Table 4**). Relevant medical history and baseline symptoms will be collected at the initial screening visit (V0) and V1, and will be graded according to the CTCAE 5.0 criteria and sent to the medical team for review. Any member of the medical team may review the medical history as part of the pre-randomization review process to clear the participant to V1. The study physician will complete a final eligibility review and sign-off prior to randomization. Adverse events will be recorded starting at every contact once the participant has started study product, which will be V2 and V3. In addition, the participant will complete a 30-day Adverse Event telephone assessment (30 days after V3, with a window of +/- 7 days) to follow up on any ongoing adverse events only.

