Participants will be instructed to smoke *ad libitum* prior to this session. Prior to the session, the participant will be asked to complete basic demographics, smoking, tobacco product use, and health history questionnaires used in our previous studies  that will be reviewed and approved for eligibility by a licensed medical provider following the visit. CC, SREC, and other tobacco product use eligibility criteria will be evaluated using a timeline follow back procedure  and smoking history measures used in previous studies . These questionnaires may be pushed by our institutional Qualtrics server to be completed electronically (via text or email) prior to the session. Current major depressive disorder (MDD) and suicidality will be identified using the Patient Health Questionnaire (PHQ-9; see Appendix L) . The screening session and the three return visits are each expected to last approximately 3 hours. The final safety telephone call will assess any ongoing adverse effects and should last approximately 10 minutes.

**COVID-19 adaptation:** Eligible participants will be scheduled for a virtual screening session using an institutionally approved platform, such as Zoom. If we are unable to collect any required biological specimens through mail, the participant may be asked to go in-person to conduct the tests through an approved collection site. Approved sites may include University of Texas MD Anderson, University of Texas sister institutions including the Center for Neurobehavioral Research on Addiction (CNRA) at University of Texas Medical School, other universities or hospitals located in Texas, and/or contracted commercial vendors.

**Baseline Medical Clearance.** Following the completion of the baseline visit, a member of the medical team (Physician assistant and/or the Physician) will review all relevant data collected at screening and will provide their clearance for the participant to proceed to Visit 1. The study Physician will have the final review of the data and will complete the final eligibility sign off prior to randomization. In the event the Physician is not able to sign-off prior to the visit (due to being out of office), the Principal Investigator may provide the initial sign-off so that the visit may proceed, and the physician will sign-off upon their return.

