**Adverse Event Safety Assessment.** 30 days (+/- 7 days) following the end of Phase 3, study participants will complete a telephone visit with study staff to assess ongoing adverse events.

**Post-study smoking cessation treatment.** We will offer all participants 8 weeks of free smoking cessation treatment, which may include nicotine replacement therapy (NRT; nicotine patch and lozenge) and smoking cessation counseling, at the end of their study participation. Alternatively they may be referred to another smoking cessation study. It is not the intention of this phase of study to evaluate the efficacy of EC for smoking cessation, but rather to facilitate smoking cessation by offering free treatment at the conclusion of EC exposure. This fulfills what we see as a strong ethical obligation to treat smokers that enter our research programs. NRT and counseling will be administered by MD Anderson's Tobacco Treatment Program (TTP), headed by Drs. [name] (Co-I) and [name] (Co-I), which provides free treatment to all

**Table 2.** Project measurement, by time point.

Week	-1	0	2	4	6	10
Visit	T0	0	1	2	3	T1
Telephone contact	x					x
In-person or virtual Session		x	x	x	x	
Initial baseline measures:						
Initial eligibility screen (e.g., age, nicotine product use)	x					
Demographics, smoking, tobacco product use, and health history		x				
PHQ-9	x					
Tobacco Products and Risk Perceptions Survey (TPRPS)	x					
Environmental Tobacco Smoke Exposure Questionnaire (ETSEQ)	x					
Product Use:						
Timeline Follow Back (TLFB) of CC & other product use	x	x	x	x	x	
Timeline Follow Back (TLFB) of SREC use			x	x		
Urine sample to measure nicotine, cotinine, nicotelline and anabasine		x	x	x		
Smartphone EMA of product use 	x	x	x	x		
Ongoing Adverse Event (AE) Assessment			x	x	x	
Health Changes Questionnaire		x	x	x		
Product Acceptability:						
Product Evaluation Scale (PES) - CC	x	x	x	x		
Product Evaluation Scale (PES) - SREC			x	x		
Perceived Health Risk Questionnaire (PHRQ) – CCs & ECs	x	x	x	x		
Perceived Health Risk Questionnaire (PHRQ) – SRECs			x	x		
Implicit Association Test (IAT) – CCs & ECs	x	x	x	x		
Brief Smoking Consequences Questionnaire-Adult (BSCQ-A)	x	x	x	x		
EC-specific Brief Smoking Consequences Questionnaire-Adult (EC-BSCQ-A)	x	x	x	x		
Product Reinforcement:						
Purchase task (PT) - CCs	x	x	x	x		
Purchase task (PT) - SRECs			x	x		
Respiratory Health and Symptoms						

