- Unless otherwise noted, the Oncore SAE report form will be utilized for safety reporting to the IND Office and MDACC IRB.
- Serious adverse events will be captured from the time of the first protocol-specific intervention, until 30 days after completing the study participation, unless the participant withdraws consent. Serious adverse events must be followed until clinical recovery is complete and laboratory tests have returned to baseline, progression of the event has stabilized, or there has been acceptable resolution of the event.
- Additionally, any serious adverse events that occur after the 30 day time period that are related to the study participation must be reported to the IND Office. This may include the development of a secondary malignancy.

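### The one safety contact after the last visit is limited to ongoing adverse events, although the plan commits to AE monitoring and SAE capture to 30 days, so new events after V3 are not actively sought

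*Combined protocol and SAP*

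**What the plan says.** Three places describe the final call.

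- Specific Instructions for Adverse Events Recording first says when AEs are recorded: "Adverse events will be recorded starting at every contact once the participant has started study product, which will be V2 and V3". It then adds one call, "30 days after V3, with a window of +/- 7 days", whose purpose is "to follow up on any ongoing adverse events only".
- Procedures, under Adverse Event Safety Assessment, places the call "30 days (+/- 7 days) following the end of Phase 3" and says "study participants will complete a telephone visit with study staff to assess ongoing adverse events".
- Procedures, in the description of the screening session (V0), says: "The final safety telephone call will assess any ongoing adverse effects and should last approximately 10 minutes".

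Two places state how long events are captured.

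- Adverse Events and Serious Adverse Events: "Adverse event monitoring will continue up to 30 days after medication is completed". The same section defines an adverse event as something that either appears or gets worse after product is started, so new onset counts.
- The section on SAE reporting: "Serious adverse events will be captured from the time of the first protocol-specific intervention, until 30 days after completing the study participation". Withdrawal of consent is the one exception given.

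**The concern.** A 30-day capture period that includes new events needs at least one contact that asks about them. The protocol has a single scheduled contact in that period and restricts it to ongoing events. Staff who follow the recording instructions as written would have no direction to ask whether anything new has happened since V3.

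What is at stake is the completeness of post-product safety data. The protocol says that e-cigarettes may cause lung injury or other serious health problems and that its team will watch for these. It also sets six-monthly IRB and DSMB review because of safety information on vaping. Reviewers would read post-product counts as the yield of capture to day 30, when for new events those counts rest on volunteered or incidental reports.

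The crossover adds an asymmetry. The product used in Phase 2 has two more weeks with solicited AE recording, up to V3. The product used in Phase 3 has no solicited follow-up for new events once it stops. Because order is randomised 1:1 and counterbalanced, this points to under-ascertainment overall rather than to a bias between nicotine and placebo.

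**Working it through.** No power, sample size or alpha figure is involved. The check compares the sections and does calendar arithmetic on the stated window.

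**1. Is there another contact after V3 that would pick up new events?**

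- Smartphone assessments run for 42 days, which is 6 × 7 and so ends at week 6, the time of V3. They cover product use and dependence symptoms.
- The respiratory questionnaire is completed at visits, and a raised score is taken up at the next visit. There is no visit after V3.
- Smoking cessation treatment is offered at the end of participation. It is optional, may be replaced by a referral, and has no AE questioning described within it.
- The telephone call is therefore the only planned safety contact.

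**2. What does the call cover?** Two readings are possible.

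- *Strict:* the call follows up events already on record at V3. The word *only*, joined to the idea of following up, supports this. Every event starting between V3 and the call is then unsolicited.
- *Broad:* the call covers any event present on the day. The two statements in Procedures, which lack *only*, allow this. An event that starts after V3 and persists would be picked up. One that starts and resolves before the call would not.

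New events after V3 are not fully solicited under either reading.

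**3. When can the call fall?**

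- Earliest: 30 − 7 = day 23 after V3.
- Latest: 30 + 7 = day 37.
- Nominal in Table 2: week 10 − week 6 = 4 weeks = day 28, inside the window.
- Time left to day 30 after the call: 30 − 23 = 7 days at most, and 30 − 28 = 2 days on the Table 2 schedule. It is none if the call falls on day 30 or later.

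**4. From what date do the 30 days run?** Four anchors are used: V3, the end of Phase 3, the end of medication, and completion of study participation. The first three may nearly coincide. The fourth need not. If the call itself counts as participation, the SAE period would end between 23 + 30 = day 53 and 37 + 30 = day 67 after V3, with no planned contact in it.

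**5. Effect of the change.** A call that also asks about new events but takes place on day 23 covers 23 of 30 days counted from V3. The same call on day 30 or later covers 30 of 30.

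**The case against.** The strongest reply is that nothing bars a new event from being recorded. An SAE must reach the IND Office within 24 hours of being known, whatever its attribution, and related SAEs stay reportable after 30 days. AEs during Phase 3 product use are solicited at V3. Participants who take up cessation treatment meet staff of the program whose clinicians manage AEs. All of this stands, and it confines the gap to active solicitation of events that start after V3. It does not close the gap, because the reporting duty depends on knowledge that the one scheduled contact is not directed to seek.

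It can also be said that *ongoing* means continuing assessment, as the Table 2 row label might. That is possible for the table, but *only* in the recording instructions does not fit it. The call script and the Data and Safety Monitoring Plan referred to under Protection against Risks are not in the text supplied, so practice may be better than the wording.

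Two stronger readings are tempting and are not supported.

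- A reader might infer that the window contradicts the 30-day period. It does not. It closes on day 37, and the limit for AEs can be read as a ceiling. The wording for SAEs is firmer, but the most that follows is that a call may take place too early to cover the whole period.
- A reader might express the gap as a share of follow-up: 30 of 28 + 30 = 58 days (52%) for the post-product period, or 7 of 30 days (23%) after a day-23 call. These are shares of calendar time, more than half of it off product in the first case, and not shares of events missed. They also overlap: if the call never asks about new events, its date makes no difference to them.

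**Conclusion.** The conflict is real and should be resolved. The plan commits to AE monitoring and SAE capture over a period that includes new events, and restricts the only planned contact in that period to ongoing ones. Events starting after V3 are recorded only if volunteered or otherwise learned of. Those that resolve before the call are exposed on either reading of *ongoing*, and those that persist to the call are exposed on the strict reading. The timing of the call is a secondary point: up to 7 days may remain before day 30 when it is made.

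The number of events affected cannot be estimated from the documents. The consequence is limited to safety ascertainment. The primary outcome is unaffected, and the statistical section plans no AE analysis. The conclusion assumes that the call follows the protocol wording and that no safety document outside the supplied text directs staff to ask about new events.

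**What to change.** Reconcile the five places quoted above.

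- **Scope.** Delete the restriction to ongoing events in the recording instructions and in both descriptions under Procedures. State that the call asks about any new AE or SAE since V3, including one that has resolved, as well as the status of ongoing events. Make the call script match.
- **Start point.** Name one common date from which the 30 days run for AEs, SAEs and the call, and say whether the call counts as study participation.
- **Window.** Either open it no earlier than day 30 from that date, or keep it and state that solicited capture ends at the call, with later events recorded as reported. Align the Table 2 column with the choice.

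The cost is a wording amendment, one or two questions in a call already planned at about 10 minutes, and a slightly later call for some participants if the window is moved. No extra contact is needed.
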